8.1.2 Randomization and stratifications

All patients entered will be centrally registered at the EORTC Headquarters (for practical details, see Chapter on randomization procedure). The Pocock and Simon Minimization with Biased-coin Assignment methodology [Ref. 73] will be utilized to perform subject randomization for this study. Per suggestion of the ICH E9 statistical guidelines, the algorithm has been modified to incorporate a random allocation component in order to ensure 15% of completely random assignments. Stratification factors are: stage (IB vs II vs IIIA), adjuvant chemotherapy (no adjuvant chemotherapy versus adjuvant chemotherapy), PD-L1 status: negative (TPS=0%) versus weak positive (TPS = 1-49%) - versus strong positive (TPS≥50%) and regions (Western Europe versus Eastern Europe versus Rest of the world versus Asia). Minimization algorithm separately applied for each PD-L1 status, to ensure an optimal balance of treatment arms within each PD-L1 level.

Treatment allocation will be blinded (see Chapter 14).

Note: Tumor staging is based on TNM stage (according to the 7th edition of the TNM classification for lung cancer).

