8.2.3 Statistical methods

8.2.3.1 Efficacy endpoints

The primary analyses of the primary and secondary efficacy endpoints (DFS, OS and LCSS) will be performed on all randomized patients according to the intention to treat (ITT) principle.

Estimates and confidence intervals

Estimates of the median DFS, OS and LCSS will be obtained by the Kaplan Meier technique. The 95% confidence interval (CI) for the median will be calculated using the reflected CI method.

Estimates of the event-free rate at a fixed time point will be obtained using the Kaplan Meier technique and 95% CI will be calculated by the Greenwood's formula for standard deviation. Estimates of hazard ratios and their 95% CI will be obtained by Cox regression. Kaplan Meier curves will be drawn for both the experimental and control arms on the same plot.

Inference

The DFS and OS will be analyzed by a Cox Proportional Hazard Regression with treatment adjusted by the following covariates: stratification factors including stage, PD-L1 IHC expression, adjuvant chemo, regions, and additional factors including histology and smoking status. Permutation test [Ref. 74] will be used as a primary test for DFS to compare the experimental versus the control arm. The Wald test without permutation of allocation sequence will be used as a supportive analysis for DFS, but as a primary test for OS. The hazard ratios and corresponding 95% CIs will be estimated using the multivariate Cox regression model stated above (using Efron's tie-handling method). A sensitivity analysis will include sex (male vs. female) and age (<65 vs. ≥ 65 years) as additional adjustment factors in the Cox regression model. A logrank test with no adjustment factors to compare the two arms will also be performed as a sensitivity analysis.

If a randomized patient is not disease free at baseline, the date of randomization will be used as the date of event for the primary DFS analysis in the PD-L1 strong positive, PD-L1 positive and the whole population.

Analysis of LCSS will be based on the log-rank test and Cox regression model. Competing risks approaches such as cumulative incidence function (CIF), Gray's test, Fine-Gray subdistribution hazard model, etc., will also be performed, where deaths from other causes are considered as competing risks. As no Type I error control is applied to LCSS, the p-values for LCSS analyses, if provided, are nominal only and for descriptive purpose.

Table 10. Analysis Strategy for Key Efficacy Variables

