Endpoint/Variable (Description, Time Point)	Primary vs. Supportive Approach†	Statistical Method‡	Analysis Population	Missing Data Approach
Primary/dual-primary Endpoints				
DFS	P	Permutation test with multivariate Cox regression model§	ITT ◆ all patients, ◆ PD-L1 strong positive ◆ PD-L1 positive	Model-based
	S	Wald test in multivariate Cox regression model Non-adjusted logrank test	ITT ◆ all patients, ◆ PD-L1 strong positive ◆ PD-L1 positive	Model-based
Secondary Endpoints				
OS	P	Wald test in Multivariate Cox regression model	ITT ◆ all patients, ◆ PD-L1 strong positive ◆ PD-L1 positive	Model-based
LCSS	P	Non-adjusted logrank test	ITT ◆ all patients,	Model-based
† P=Primary approach; S=Secondary approach. ‡ Statistical models are described in further detail below: § Adjusted by Stage (IB versus II versus IIIA), PD-L1 IHC expression (0 versus 1-49% versus ≥ 50%), Adjuvant Chemo (No chemotherapy vs. adjuvant platinum-based chemotherapy), Histology (squamous vs. non-squamous), smoking status (smokers vs. non-smokers), and regions (Western Europe versus Eastern Europe versus Rest of the world versus Asia).				

The strategy to address multiplicity issues with regard to multiple endpoints and interim analyses is described in Section 8.3, Interim Analyses and in the below subsection on Multiplicity.

[figure not shown]

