8.2.4 Pre-planned sensitivity or exploratory analyses

In addition to the analyses mentioned in the previous section, the following sensitivity analyses may also be performed:

- ◆ using the ITT population, but considering the stratification factor - Stage (AJCC V7) information as indicated on the CRFs based on pathology report(s). Stage information based on AJCC V8 converted from AJCC V7 and additional information collected in the database may also be considered.
- ◆ For the randomized patient not disease-free at baseline, the date of randomization is used as the censoring date for DFS analysis.

- ◆ Proportional hazard assumption will be checked. If the data clearly do not follow proportional hazards, medical explanations should be identified and alternative statistical methods will be explored.
- ◆ Sensitivity analyses for DFS may also be conducted, adjusted by complete resection status (complete resection vs. uncertain) as assessed and described by the quality assurance for surgery [Ref. 86].

Subgroup analyses are planned to compare DFS by treatment arm in the stratification factors. In addition, subgroup analyses by histology, smoking status, sex and age are also planned. Two cut-off values for age (70 years and 75 years) to define elderly population will be explored to assess the impact of geriatric domains on study primary/dual-primary endpoints and PD-L1 status. Subgroup analyses by complete resection status (complete resection vs. uncertain) as assessed and described by the quality assurance for surgery [Ref. 86] may also be conducted.

The above analyses will be repeated for the secondary endpoint OS.

Exploratory analysis: factors related to the cure rate

Cure rate, defined as proportion of patients who are still alive when the OS curve reaches plateau- will be explored. Any conclusion on cure rate should incorporate all subgroups (mature and less mature observations with respect to the terminal plateau) and consistency check will be performed to examine subgroups with less mature observations if the same conclusion can be drawn for those subgroups.

Proportion of PD-L1 status

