2.3 Date of death is taken from end of treatment form, **eofform** (dtsof, ssof=2) or follow up form, **fuform** (dtssfu, ssfu= 2) or survival sweep form **sweepform** (dtssweep, sssweep = 2)

2.4 Date of last disease evaluation is taken from the following:

- ◆ - Date of randomization
- ◆ - IMASS form, **imassform**(dtmethod1,dtmethod2,dtmethod3, maximum).

In each patient without DFS event, the max of those dates will be used as date of censoring.

2.5 Date of last known to be alive is taken from the last dates of the following forms (dates):

- ◆ Date of last disease evaluation as in (2.4)
- ◆ **formFAT** (dtsurfat, dtrtfat, dtst1fat, dtst2fat, dtst3fat, dtst4fat, dtst5fat, dtst6fat, dtst7fat, dtsp1fat, dtsp2fat, dtsp3fat, dtsp4fat, dtsp5fat, dtsp6fat, dtsp7fat)
- ◆ **formEOT** (dtsof, dtnew)
- ◆ **formLBBIO** (dtbio and nybio = 1)
- ◆ **formLBHEM** (dthem and nyhem = 1)
- ◆ **formLBTHY** (dtthy and nythy = 1)
- ◆ **formLBURI** (dtLBURI and nyLBURI = 1)
- ◆ **formTRT** (dttrt and nytrtadm=1)
- ◆ **formSWEEP** (dtssweep and sssweep in (1,2))
- ◆ **formFU** (dtssfu)
- ◆ **formAE** (aestdc, aeendtc)

In each patient without OS event, the max of the above dates will be used as date of censoring.

2.6 Date of death due to NSCLC is taken from end of treatment form, **eofform** (dtssof, ssof=2 and rdeadof=1) or follow up form, **fuform** (dtssfu, ssfu= 2 and rdeadfu =1) or survival sweep form **sweepform** (dtsssweep, sssweep = 2 and) when cause of death is PD (**eofform** [dtssof, ssof=2] or **fuform** [dtssfu, ssfu= 2]). If cause of death is missing, not defined or not available then such case will be treated as censoring at the date of death.

3. Disease free survival endpoint

Disease free survival considering the following event or censoring:

- ◆ Date of recurrence (2.1)
- ◆ Date of secondary malignancy (2.2)
- ◆ Date of death (2.3)
- ◆ Censoring: In the absence of event, date of last disease evaluation (2.4).

Disease Free Survival (DFS) is calculated as the time from randomization to either the date of disease recurrence or the date of death (whatever the cause). Patients alive with no evidence of disease recurrence at the time of their last visit are censored at the time of the last examination.

Therefore, DFS is the time between the date of randomization and the earliest date among of events or censoring as described in 2.1, 2.2, 2.3 and 2.4.

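### LCSS, a descriptive secondary endpoint, has an unadjusted log-rank as primary analysis although allocation is minimised on four factors and OS is adjusted; no visible analysis varies how deaths of unknown cause are attributed

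*Combined protocol and SAP*

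**What the plan says.** **Method.** Table 10 (section 8.2.3.1) has a single LCSS row: primary approach, ITT, all patients, "Non-adjusted logrank test". For OS the primary approach is a Wald test in the multivariate Cox model. For DFS the unadjusted log-rank is only supportive. The covariate list (stage, PD-L1, adjuvant chemotherapy, region, histology, smoking) is introduced for two endpoints only: "The DFS and OS will be analyzed by a Cox Proportional Hazard Regression with treatment adjusted by the following covariates". For LCSS the text says "Analysis of LCSS will be based on the log-rank test and Cox regression model", without covariates. It adds competing-risk analyses, "where deaths from other causes are considered as competing risks".

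**Status.** "As no Type I error control is applied to LCSS, the p-values for LCSS analyses, if provided, are nominal only and for descriptive purpose".

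**Allocation.** Section 8.1.2 uses "The Pocock and Simon Minimization with Biased-coin Assignment methodology", with 15% random assignment, applied separately within each PD-L1 level.

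**Unknown cause of death.** Appendix N, 2.6: "If cause of death is missing, not defined or not available then such case will be treated as censoring at the date of death". Appendix N, section 5, records a patient who died but had no NSCLC death under 2.6 as censored in the primary analysis and as a competing event in the supporting one. Section 8.2.4 closes its list of sensitivity and subgroup analyses with "The above analyses will be repeated for the secondary endpoint OS"; LCSS is not mentioned.

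**The concern.** Minimisation balances the arms on factors expected to be prognostic. An analysis that ignores those factors keeps their variation in its standard error, so it discards part of the precision that the allocation has bought. The plan recognises this for DFS and OS but not for LCSS. If the LCSS Cox model is also unadjusted, readers will set a marginal LCSS hazard ratio beside a conditional OS hazard ratio as if the two were comparable.

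The second issue concerns attribution. A death of unknown cause never counts as a lung cancer death, even after a recurrence documented on the recurrence form. The competing-risk methods change how other-cause deaths are treated; they do not change what an unknown cause is taken to be. A reader therefore cannot see how far LCSS depends on the rule.

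No trial decision rests on LCSS. What is at stake is the precision and clarity of a reported secondary result.

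**Working it through.** The documents give no LCSS event count, hazard ratio or power, so there is no LCSS figure to reproduce. As a check of the power formula on the nearest stated figure, 551 DFS events at HR 0.75 give 87.2% at one-sided 1.25% (stated as about 86%) and 92.2% at 2.5% (stated as about 92%).

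**1. A plausible level for LCSS.** Every lung cancer death is a DFS event, so LCSS cannot lie below DFS. With exponential DFS and the design medians of 42 and 56 months:
- control: 0.5^(60/42) = 37.1% at 5 years;
- experimental: 0.5^(60/56) = 47.6%.

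LCSS must also leave room for patients alive after recurrence, other-cause deaths and second malignancies. I use 60% and 70% (assumed).

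**2. What adjustment gains.**
- From the documents: N = 1180, Table 7 accrual, OS HR 0.765 as a stand-in, 1% yearly drop-out, 15% random assignment.
- Assumed: 5-year LCSS 60%, cut-off at month 90, other-cause mortality 1% per year, the stage mix, and a stage contrast taken from the 40/66/75% in section 1.1, in full or halved on the log scale.
- Result: about 404 events. Adjusting for stage gains about 0.3 to 1.1 power points, equal to about 1-3% more events.

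Check by formula: z = 0.2679 x sqrt(404)/2 = 2.692, so power = Φ(2.692 - 1.960) = 76.8%. With 1% more events it is 77.2% and with 3% more it is 78.0%, that is +0.4 and +1.2 points, which agrees.

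The gain depends on the stage mix. Repeating the simulation with IB at the 35% cap of section 4.1.3 (mix 35/40/25) and the full contrast gave about 2.0 points (about 6% more events); with the contrast halved it gave 0.6.

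**3. Level and hazard ratio.** In 8,000 simulated null trials per scenario, with assumed stage HRs of 1.6 and 2.6 against IB, two-sided 5% rejection was 5.2% (log-rank) and 5.7% (adjusted Cox). With all log-hazards doubled it was 3.9% and 5.3%. The Monte Carlo SE is sqrt(0.05 x 0.95/8000) = 0.24 points. At a conditional HR of 0.75, the unadjusted and adjusted estimates were 0.753 and 0.748, and with doubled log-hazards 0.766 and 0.749.

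**4. Unknown cause, level of LCSS.** Let u be the share of deaths with unknown cause, constant over time and across causes (assumed 5-15%). Under 2.6 the Kaplan-Meier estimate tends to S^(1-u):

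| True 5-year LCSS | u = 5% | u = 15% |
|---|---|---|
| 60% | 0.60^0.95 = 61.6% | 0.60^0.85 = 64.8% |
| 70% | 0.70^0.95 = 71.3% | 0.70^0.85 = 73.8% |

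If all unknown-cause deaths count as lung cancer, the estimate tends to S x exp(-5uμ). At S = 60% and other-cause mortality μ = 1% per year this is 59.9% (u = 5%) to 59.6% (u = 15%).

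**5. Unknown cause, hazard ratio.** Under 2.6 the LCSS hazard ratio is multiplied by (1-u_E)/(1-u_C), where E is pembrolizumab and C placebo. Equal shares leave 0.765 unchanged. With 15% against 10% it becomes 0.765 x 0.85/0.90 = 0.723. Counting all unknowns as lung cancer, with 80% of control deaths from lung cancer and an other-cause HR of 1 (both assumed), gives (0.612 + 0.15 x 0.2)/(0.8 + 0.10 x 0.2) = 0.783.

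**6. Competing-risk analysis.** With λ = -ln(S)/5 and μ = 1% per year:
- unknown cause as a competing event (section 5): 5-year incidence = (1-u) x λ/(λ+μ) x [1 - exp(-5(λ+μ))];
- unknown cause as censored (2.6): λ/(λ+μ) x [1 - exp(-5(1-u)(λ+μ))].

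At S = 60% these give 37.1% and 37.6% (u = 5%), and 33.2% and 34.5% (u = 15%). At S = 70% they give 27.8% and 28.1%, and 24.9% and 25.6%. The gap is about 0.3 to 1.3 points.

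**The case against.** **The endpoint is descriptive.** With no alpha and no visible power target, a gain of about one power point has no decision attached, and the hazard ratio hardly moves under moderate prognostic effects. This stands, and it is why the point is minor. The change to Table 10 is still worth making because it is specific and costs almost nothing.

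**A Cox model for LCSS is already planned.** True, so an adjusted analysis may exist as support. What is missing is the statement that it is adjusted. The sentence on estimating hazard ratios from the multivariate model sits in the DFS and OS paragraph, and its reach to LCSS is unclear.

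**Appendix N need not contradict itself.** One can read 2.6 as the primary-analysis rule and section 5 as supplying the competing-risk handling. That is fair: no contradiction is forced. However, the section 5 sentence opens with deaths from causes other than NSCLC, which an unknown cause need not be, so one clause would settle it.

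**The unknown share is assumed.** It is; the documents give none. The textual gap does not depend on it, but its size does.

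**Stronger readings that the documents do not support.** A reader might infer that a log-rank under minimisation is invalid or inflates the error rate; step 3 shows it close to nominal or conservative. A reader might also take the 5-year figures of section 1.1 as this trial's LCSS and obtain much larger distortions. Even with 35% stage IB and no IIIA, those figures give only 0.35 x 60% + 0.65 x 34% = 43.1%, inside the 37.1-47.6% range of design DFS, and any IIIA share lowers it. That leaves almost no room between LCSS and DFS. They serve here only for the contrast between stages. Finally, section 8.3 and Tables 8 and 9 are blacked out, so the statement can only be that no visible analysis varies attribution.

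**Conclusion.** The concern holds as a minor one. The primary LCSS test is valid but leaves out factors on which allocation was minimised. The loss is about 0.3 to 1.1 power points (about 1-3% of events) at an assumed 5-year LCSS of 60%, and about 2 points in the stage mix and contrast most favourable to adjustment. Whether the LCSS hazard ratio is comparable with the OS hazard ratio is not stated.

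The unknown-cause rule is a reasonable main rule. At an assumed 5-15% share it would raise a 5-year LCSS of 60% by 1.6 to 4.8 points and one of 70% by 1.3 to 3.8 points. It distorts the hazard ratio only if the shares differ between arms, and nothing in the documents says that they do. The ambiguity in the competing-risk analyses is worth about 0.3 to 1.3 points of 5-year incidence. All these sizes rest on the assumed LCSS level, prognostic contrast, unknown share and other-cause mortality.

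**What to change.** 1. In Table 10, make the Cox model adjusted for the footnoted covariates (Wald test, as for OS) the primary LCSS approach and list the unadjusted log-rank as supportive. In section 8.2.3.1, state that the LCSS hazard ratio uses the same covariates.
2. Keep 2.6 as the main rule. In Appendix N, state one handling of unknown-cause deaths for the cumulative incidence, Gray and Fine-Gray analyses, so that 2.6 and section 5 read the same way.
3. Add a sensitivity analysis that counts unknown-cause deaths as lung cancer deaths, in two versions: all of them, and only those after a recorded recurrence. Tabulate unknown-cause deaths by arm.

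The cost is wording in Table 10, section 8.2.3.1 and Appendix N, one sensitivity analysis and one table, using recurrence and cause-of-death fields already on the CRF. LCSS carries no alpha, so error control for DFS and OS is unaffected.

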8.2.3.2 Toxicity

Analysis for toxicity is based on the safety population. The worst grade of toxicity/adverse events observed over the whole treatment period according to CTCAE version 4.03 will be displayed. In the primary analysis, no formal statistical analysis will be performed to compare toxicity between arms.

8.2.3.3 Multiplicity

The family-wise error rate (Type I error) for DFS and OS hypotheses is strongly controlled at 2.5%, one-sided. The study uses the graphical method of Maurer and Bretz [Ref. 75] to provide strong multiplicity control for multiple hypotheses as well as interim efficacy analyses. See Figure 3 for an overview of the multiplicity strategy.

Figure 3: Multiplicity Graph for Alpha Re-allocation Strategy

[figure not shown]

Bonferroni adjustment is adopted, by initially splitting alpha equally to test DFS, i.e. 1-sided alpha = 1.25% is allocated to the whole population and 1-sided alpha = 1.25% is allocated to the PD-L1 strong positive. The graphical method is then applied to determine the multiple testing procedures. If the null hypothesis of DFS is rejected in PD-L1 strong positive subgroup, its alpha is fully reallocated to DFS hypothesis testing in PD-L1 positive subgroup. DFS in the whole population can be tested at alpha = 2.5% when DFS hypotheses in PD-L1 strong positive and PD-L1 positive subgroups are both rejected. OS hypothesis testing in the

whole population and PD-L1 strong positive will not occur until DFS hypothesis is rejected in the whole population. Below is an illustration of possible overall alpha levels for each DFS hypothesis may be tested at.

- ◆ DFS in PD-L1++: alpha=1.25% (initial alpha assigned), or alpha=2.5% (once all three OS hypotheses are rejected).
- ◆ DFS in PD-L1+: alpha=1.25% (once DFS in PD-L1++ is rejected and OS in PD-L1++ is not rejected), or alpha=2.5% (once all other hypotheses are rejected)
- ◆ DFS in the whole population: alpha=1.25% (initial alpha assigned), or alpha=2.5% (if all other two DFS hypotheses are rejected).

Note that a Hwang-Shih-DeCani (HSD) spending function with $\gamma = -4$, determines the boundary of alpha threshold at each IAs for DFS and OS.

The threshold alphas with the expected number of events are illustrated in [Table 8](#) and [Table 9](#).

In case only one of the primary DFS hypotheses is significant at the time of IAs, then the significant result will be declared in the corresponding population or subgroup. The other primary DFS hypothesis will continuously be tested according to the maturity of the next test, by using the available nominal alpha.

In case all primary DFS hypotheses are significant at the time of IAs, then the significant results will be declared in all the respective populations. In such situation, the study will declare success in all primary hypotheses, yet the analyses for secondary endpoint will be continued as scheduled.

The above multiplicity control strategy is based on current understanding on the PD-L1 biomarker, and is subject to modification based on emerging external data on the prevalence of PD-L1 biomarkers, or the correlation between PD-L1 statuses and the treatment effect.

8.2.4 Pre-planned sensitivity or exploratory analyses

In addition to the analyses mentioned in the previous section, the following sensitivity analyses may also be performed:

- ◆ using the ITT population, but considering the stratification factor - Stage (AJCC V7) information as indicated on the CRFs based on pathology report(s). Stage information based on AJCC V8 converted from AJCC V7 and additional information collected in the database may also be considered.
- ◆ For the randomized patient not disease-free at baseline, the date of randomization is used as the censoring date for DFS analysis.

- ◆ Proportional hazard assumption will be checked. If the data clearly do not follow proportional hazards, medical explanations should be identified and alternative statistical methods will be explored.
- ◆ Sensitivity analyses for DFS may also be conducted, adjusted by complete resection status (complete resection vs. uncertain) as assessed and described by the quality assurance for surgery [Ref. 86].

Subgroup analyses are planned to compare DFS by treatment arm in the stratification factors. In addition, subgroup analyses by histology, smoking status, sex and age are also planned. Two cut-off values for age (70 years and 75 years) to define elderly population will be explored to assess the impact of geriatric domains on study primary/dual-primary endpoints and PD-L1 status. Subgroup analyses by complete resection status (complete resection vs. uncertain) as assessed and described by the quality assurance for surgery [Ref. 86] may also be conducted.

The above analyses will be repeated for the secondary endpoint OS.

Exploratory analysis: factors related to the cure rate

Cure rate, defined as proportion of patients who are still alive when the OS curve reaches plateau- will be explored. Any conclusion on cure rate should incorporate all subgroups (mature and less mature observations with respect to the terminal plateau) and consistency check will be performed to examine subgroups with less mature observations if the same conclusion can be drawn for those subgroups.

Proportion of PD-L1 status

Proportion of PD-L1 status: **negative (TPS=0%), weak positive (TPS 1-49%), strong positive (TPS≥ 50%)** will be checked when approximately 100 patients accrued. In case there is any large departure from current assumption of PD-L1 status, necessary statistical adjustment will be considered. If the prevalence of PD-L1 strong positive is lower than expected, the study design/ sample size may be adjusted based on the observed proportion of PD-L1 strong positive patients to ensure that sufficient number of PD-L1 strong positive patients will be in the study.

Quality of Life

The analyses for Quality of life are defined in Section 10.5.

